#### G. Post Therapy Review (day 57)

- Face-to-face meeting and feedback
- Collection of participant data sheets
- Participant subjective overall assessment

### Data Analysis

The pre and post sleep studies will be performed using WatchPAT.  
Parameters recorded: saturation, AHI, snoring sound parameters.

AHI will be identified and analyzed by WatchPAT data and software. The WatchPat is an approved FDA sleep study device with 510K - K161579. Snoring will be quantified subjectively by both the bed partner using a visual analog score, and objectively during the home sleep study as frequency of snores (number of snores / hours of sleep) and % total sleep time spent snoring. Sleep quality will be quantified subjectively by PSQI score. Sleepiness will be quantified subjectively by ESS score.

### Snoring Sound

- 1) Objective: WatchPat Sleep study: Comparative analysis of % total sleep time spent snoring will be undertaken between the 2 day sleep study pre and post therapy phase. To ensure consistency, the WatchPAT microphone will be placed in the same position, just below the suprasternal notch, in both pre and post sleep studies.
- 2) VAS: Partner reported change will be assessed using VAS. Therapy efficacy will be based on statistical analysis of average VAS scores for the three periods – pre-therapy (2 weeks), therapy phase (last 2 weeks) and follow up phase (2 weeks).  
Although data will be collected for the whole of the six-week therapy phase, comparative analysis will be limited to the last two weeks of the therapy phase to exclude any transitional changes. The six-week therapy stage data will undergo temporal analysis to establish if there is a progressive change in the indices measured.
- 3) Number of nights sleeping together recorded in Subjective sleep quality questionnaire will be assessed for the pre-therapy, therapy phase and follow up phase.

### Sleep Quality

- 1) Epworth sleepiness score will be assessed for both Snorer and Bed partner for the pre-therapy, therapy phase and follow up phase.
- 2) Pittsburgh Sleep Quality Index will be assessed for both Snorer and Bed partner for the pre-therapy, therapy phase and follow up phase.

- 3) Subjective sleep quality questionnaire will be assessed for both Snorer and Bed partner for the pre-therapy, therapy phase and follow up phase.

### **See Appendix 1 for endpoint assessment and validation**

#### Safety

- 1) Any side effects or adverse events to be recorded in research record sheets and will be collated for assessment
- 2) Pre and post therapy WatchPat sleep studies will be assessed for change in parameters of saturation and AHI.
- 3) The pre and post oral examination clinical sheets will be scrutinized for any change in oral status.

#### Statistical Considerations

Sample size: 50 participants

Data will be analyzed based on two tailed paired t-test, with 80% power.  $P < 0.05$  will be considered significant. Multiple regression analysis will be used to identify which of the following factors has a causal relationship with the outcome - age, sex, BMI, neck size, AHI group (<5 and 5-15) and clinical examination characteristics (Endoscopy staging, Muller Maneuver, Friedman Classification, Tonsil size)

Power analysis:

- AHI reduction >50% and AHI <10: sample size required 17,
- VAS change of 40%, (i.e. average snoring score to drop from 6.4 to 3.8 on 10 point scale): sample size required 4. Standard deviations extrapolated from Verse et al..
- To calculate the required sample size for the paired observations of pre and post treatment for proportion of sleeping time snoring more than 40 dB; first the correlation between proportions before and after treatment was estimated by using provided pilot data. The required sample size of the patients with snoring more than 40 dB was then calculated such that the one-sided statistical test would be able to detect 20% reduction in snoring time from 50% to 30% with 80% power. (See Appendix 1 for validation of parameters)

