### 7. BACKGROUND AND SIGNIFICANCE

Forty five percent of the male population snore, 25% habitually (daily). Sleep disordered breathing (SDB) (partial or total obstruction of the upper airway during sleep) is a spectrum of conditions (Fig 1) ranging from simple snoring to obstructive sleep apnea-hypopnea syndrome (OSAHS). The latter affects at least 4-6% of the population and is associated with increased incidence of hypertension, cardiac (heart attacks) and cerebral events (strokes). Although the gold standard of treatment for OSAHS is Continuous Positive Airway Pressure (CPAP), a variety of treatments are offered for simple snoring.

[figure not shown]

Figure 1: spectrum of sleep disordered related breathing ranging from simple snoring to severe obstructive sleep apnea syndrome (OSAHS: obstructive sleep apnea hypopnea syndrome, CPAP: continuous positive airway pressure)

Although there are several lifestyle practices associated with snoring (smoking, obesity, drinking etc.), a significant proportion of individuals may snore despite not being associated with these.

The most notable change that occurs in the physiology of humans during sleep is the reduction in the tone of the muscles and increased collapsibility of the throat (pharynx) and tongue. Notably, there is evidence to show that the collapsibility is significantly higher in patients who obstruct (OSAHS) and marginally higher in patients who snore (simple snoring) when compared to individuals who don't snore (Fig 2). As demonstrated in the graph below, it has been shown that when compared to "normal" individuals, the breathing passage in snorers and sleep apnea individuals collapses at a positive rather than negative airway pressure.

[figure not shown]
[figure not shown]

Figure 2: critical closing pressure in healthy subjects, snorers and patients with OSA (SDB-1 = snorers, SDB-2 = Sleep Apnea), (according to Isono et al. 2)

Research has demonstrated that increasing the pharyngeal muscle activity or tone, reduces the collapsibility of the airway as demonstrated by the graphs below (Figure 3). It is the reduction of throat/pharynx/tongue muscle tone that leads to this partial or complete obstruction.

Redrawn from Smith and Schwartz, *Sleep Apnea: Pathogenesis, Diagnosis and Treatment*, 2002

Figure 3: Upper airway collapsibility and critical closing pressure in sleeping individuals (according to Schwartz et al.)

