## Research Method:

The study plans to investigate the change in snoring sound, sleep quality and the safe use of intraoral neuromuscular stimulation using SnooZeal device. After appropriate screening and assessment, the recruited participants will proceed through three phases of the trial. The Pre-Trial phase collects data on the pretreatment state of the participant, after which they will enter the Therapy phase where they use the device once daily for a six week period whilst continuing to record the required data. The participant will stop using the device at the end of this stage and have a follow up phase for two weeks, during which trial indices will continue to be recorded. The trial period for each participant will be 10 weeks.

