### A. Screening

Participants will be identified from Queen's Hospital, Barking, Havering and Redbridge NHS Trust. There will be a screening phone call to ensure suitability based on an inclusion criterion and offer first line information about the trial. If suitable, patients will be given a written information sheet and invited to undertake a 2 day home sleep study (using WatchPAT). If the average AHI from these 2 days is below 15/h, the participants will be invited for a clinical examination.

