## **10. HUMAN SUBJECTS**

### **Subjects**

50 primary snorers (AHI <15/hr) will be recruited from Queen's Hospital, Romford (Barking, Havering and Redbridge NHS Trust), UK.

Inclusion criteria

- Age 18 years and above (adult population) at entry into study
- Subjects must have a live-in partner as the assessment includes partners report
- More than six month history of habitual snoring (i.e. >5 days per week as reported by partner)

Exclusion criteria

- BMI > 35 kg/m^2
- AHI >15/h, i.e. evidence of moderate to severe OSA from sleep study
- ESS > 10 in participants with AHI 5-15/h (symptomatic mild sleep apnea should be treated with CPAP)
- Symptomatic nasal pathology i.e. septal deviation, nasal polyposis or chronic rhinosinusitis
- Tonsil Hypertrophy (Tonsil size – Grade 3 or greater)
- Tongue or lip piercing
- Pacemaker or implanted medical electrical devices
- Previous oral surgery for snoring
- Relevant facial skeletal abnormalities (i.e. syndromic facial deficiencies, severe micrognathia etc.)
- Oral disease/conditions (see Appendix 3)
- Any criteria that, in the opinion of the investigator, would make the participant unsuitable for the study due to inability to complete required study procedures

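### The protocol says a regression on nine observed baseline traits will show which of them are causes; as planned it can show only association

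*Protocol*

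**What the plan says.** Protocol section 9, Statistical Considerations, sets the aim of a secondary analysis: "Multiple regression analysis will be used to identify which of the following factors has a causal relationship with the outcome". The factors are "age, sex, BMI, neck size, AHI group (<5 and 5-15"), and "clinical examination characteristics (Endoscopy staging, Muller Maneuver, Friedman Classification, Tonsil size"). That makes nine: five participant characteristics and four examination findings.

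Four other places bear on the point.

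- Section 7 (Background and Significance) refers to "several lifestyle practices associated with snoring (smoking, obesity, drinking etc".
- Section 10 (Subjects) lists as an exclusion "ESS > 10 in participants with AHI 5-15/h". No equivalent sleepiness limit applies below an AHI of 5.
- Section 9 (Research Method) takes all recruited participants through a pre-trial phase, "after which they will enter the Therapy phase where they use the device once daily for a six week period".
- Section 9 (Snoring Sound) describes the objective efficacy analysis: "Comparative analysis of % total sleep time spent snoring will be undertaken between the 2 day sleep study pre and post therapy phase".

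**The concern.** A regression coefficient for a trait that was observed and not assigned has a causal reading only under explicit assumptions about confounding and selection. The protocol states an aim of finding causes but gives no such assumptions, and the word is not qualified elsewhere in the text.

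If the sentence is followed as written, a trait such as neck size or AHI group could be reported as a cause of the snoring outcome when it only travels with something else: smoking, alcohol use, or the way participants were selected.

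A softer reading, that the trait changes how well the device works, is not available either. With everyone treated, a trait associated with change may predict response to the device, or it may predict change that would have happened anyway, including regression to the mean.

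**Working it through.** The protocol gives no figure for this regression, so there is none to reproduce. The check is first of the text and then of how large a misleading coefficient could be.

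**Text**

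1. *Number of traits.* Age, sex, BMI, neck size and AHI group make 5. Endoscopy staging, Muller Maneuver, Friedman Classification and tonsil size make 4. 5 + 4 = 9.
2. *Assigned or observed?* AHI comes from the screening sleep study (section 9, A: "If the average AHI from these 2 days is below 15/h, the participants will be invited for a clinical examination"). The airway findings come from the examination at the recruitment visit (section 9, B). The others are characteristics participants bring with them. None is assigned.
3. *Comparator.* Section 9 (Research Method and D, Therapy phase) has every participant using the device. There is no untreated group.
4. *Routes to a misleading coefficient visible in the protocol.* Of the three lifestyle factors named in section 7, only obesity is represented, through BMI; smoking and drinking are not in the list. Separately, the sleepiness exclusion in section 10 applies to one of the two AHI groups only, and ESS is not in the list. The first is possible confounding and the second is selection.

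**Size of bias from an omitted factor (all correlations assumed)**

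Let trait T have no effect of its own. Let the omitted factor C have correlation r1 with T and r2 with the outcome, and let the other traits be uncorrelated with both. The standardised coefficient of T without C in the model is r1 × r2; with C in the model it is 0.

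| r1 | r2 | Coefficient of T |
|---|---|---|
| 0.3 | 0.3 | 0.09 |
| 0.3 | 0.5 | 0.15 |
| 0.5 | 0.5 | 0.25 |

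A simulation with the protocol's 50 participants and nine predictors (2,000 runs per setting) shows how often such a trait reaches P < 0.05. For r1 and r2 each at 0.3 or 0.5 the rate was 8% to 35%. With r1 raised to 0.7 it was 28% to 62%. The nominal rate is 5%.

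**Size of the ESS difference from the one-sided exclusion (ESS distribution assumed)**

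Suppose ESS has the same normal distribution in both AHI groups before selection, and scores above 10 are removed in the AHI 5-15 group only. With a continuity correction, a = (10.5 − mean)/SD, and mean ESS in that group falls by SD × φ(a)/Φ(a), where φ and Φ are the standard normal density and distribution function.

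| Mean | SD | a | Fall in mean ESS |
|---|---|---|---|
| 6 | 3 | 1.5 | 0.42 |
| 6 | 5 | 0.9 | 1.63 |
| 8 | 4 | 0.625 | 1.79 |
| 10 | 3 | 0.167 | 2.08 |
| 10 | 5 | 0.1 | 3.68 |

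This biases the AHI-group coefficient only so far as sleepiness is related to the outcome, which the protocol does not establish.

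**The case against.** The strongest reply has four parts.

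- *It is a matter of wording.* The causal phrase may be loose language for prediction, no objective or endpoint uses the regression, and confounder strategy is commonly left to a statistical analysis plan. It is true that little depends on this analysis, which is why the point is minor. But the complaint is not about missing model detail. The protocol affirmatively states a causal aim, and added detail elsewhere would leave that sentence wrong.
- *Observed traits can support causal inference under stated assumptions.* This is correct in principle. None is stated here, so the conclusion is limited to this regression as planned.
- *The illustrations are weak.* Section 7 links smoking and drinking with snoring, not with change under therapy. Neither habit can cause age or sex, so this route does not apply to all nine traits. If the AHI 5-15 group was sleepier before selection, the exclusion could narrow an ESS gap instead of opening one. The top of the ESS range (mean 10, SD 5) implies that about 46% of that group is excluded (1 − Φ(0.1)). All of this stands. The figures show what could happen and are not estimates for this trial.
- *The bias is comparable to the noise.* With 50 participants and nine predictors there are 50 − 9 − 1 = 40 residual degrees of freedom, so a standardised coefficient has a standard error near 1/√40 ≈ 0.16 (uncorrelated predictors, small R²). A bias of 0.09 to 0.25 is then about 0.6 to 1.6 standard errors. That is fair, but an imprecise coefficient is no better a basis for a causal claim.

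The protocol does not itself claim effect modification. That part of the concern guards against a likely misreading.

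**Conclusion.** The concern holds, as a minor one. The protocol assigns a regression on nine observed baseline traits, in a single treated group, a causal purpose that it gives no grounds for. This conclusion rests on the text and the design alone and needs none of the assumed numbers.

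The numbers illustrate the possible consequence. A trait with no effect could carry a standardised coefficient of 0.09 to 0.25 under assumed correlations of 0.3 to 0.5, and this bias does not shrink with sample size. The sleepiness exclusion could lower mean ESS in the AHI 5-15 group by 0.4 to 3.7 points under an assumed common ESS mean of 6 to 10 and SD of 3 to 5. The primary pre-post comparison and the sample size of 50 are unaffected.

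**What to change.** In Statistical Considerations, replace the causal phrase with wording such as *is associated with the outcome (exploratory)*. Draw no causal conclusion about any trait from this regression, including modification of the device effect.

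Adding smoking, alcohol use or ESS to the list would not make the analysis causal and is not needed for this correction. The change is one phrase, with no extra data, participants or analysis. The sponsor gives up only a claim that the analysis could not support.

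### The nine-factor regression, read at P<0.05 in at most 50 participants, would name a chance factor in about one trial in three, and cutting AHI at 5 discards roughly 30-45% of its information

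*Protocol*

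**What the plan says.** The Statistical Considerations of the protocol (section 9) fix these elements:

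- Size: "Sample size: 50 participants". No allowance for dropout is stated, so 50 is the most the regression can have.
- Main test: "Data will be analyzed based on two tailed paired t-test, with 80% power". The only significance threshold, P<0.05, follows directly after it.
- Purpose of the regression: "Multiple regression analysis will be used to identify which of the following factors" are causally related to the outcome.
- Candidates: "age, sex, BMI, neck size, AHI group (<5 and 5-15) and clinical examination characteristics (Endoscopy staging, Muller Maneuver, Friedman Classification, Tonsil size". That is nine factors: five demographic or baseline measures and four clinical examinations.
- Form of AHI: "AHI group (<5 and 5-15".

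The Screening paragraph of the same section obtains AHI as a numeric average over two home recordings, compared with a limit of 15/h. The power analysis covers AHI response, the visual analogue score (VAS) and snoring time. None of its items sizes the regression.

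**The concern.** The stated product of the regression is a list of patient features that matter for response. A list drawn from nine candidates at an unadjusted 0.05 has a sizeable chance of containing a feature that does nothing. With 50 participants there are only about 50/9 = 5.6 observations per factor, so real but modest factors are also likely to be missed. Reducing AHI to two groups weakens the chance of detecting a gradient in one of the most obvious candidates.

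At stake is how the results are used afterwards. A named factor could be taken as a guide to who benefits from the device.

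The concern does not depend on the causal wording in the same sentence. If the sentence claimed only association, the false-factor rate and the loss of AHI information would be the same.

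**Working it through.** **Plan's own figure.** The protocol gives no sample size, power or error rate for the regression, so there is nothing to reproduce.

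**Inputs from the protocol.** Nine factors, n at most 50, threshold 0.05, AHI split at 5 within 0-15/h.

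**Assumptions.** One outcome, one test per factor, factors named by their own p-value, no overall test first, and no factor with a true effect.

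**Step 1: chance of naming a false factor.**

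- Independent tests: 1 - 0.95^9 = 0.370, or 37%.
- Expected number of false factors: 9 × 0.05 = 0.45 per outcome.
- Simulated null linear regressions (nine predictors, sex and AHI group binary, 6,000 runs per setting) gave:

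| Correlation among factors | n = 50 | n = 40 |
|---|---|---|
| none | 33.8% | 33.6% |
| 0.3 throughout | 33.7% | 32.4% |
| 0.5 throughout | 32.9% | 32.7% |
| assumed anatomical pattern | 30.8% | 31.8% |

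The range is 31-37%, and it changes little with the correlation assumed or with some loss of participants.

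**Step 2: effect of an overall test.** In the same simulations, naming a factor only when the overall F test is also significant at 0.05 gave 4.5-5.5%.

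**Step 3: what the design can detect.** From the noncentral F with 1 and n - 10 degrees of freedom, 80% power at 0.05 needs a factor with a partial R-squared of 0.14 at n = 50, or 0.17 at n = 40. At a Bonferroni level of 0.05/9 = 0.0056 these become 0.22 and 0.27.

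**Step 4: information kept by the AHI split.** For a linear effect, the share kept is the squared correlation between AHI and the group indicator. Suppose AHI is uniform on 0-15:

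- One third of participants lie below 5 (mean 2.5) and two thirds above (mean 10).
- Between-group variance: (1/3)(2/3)(7.5)^2 = 12.5.
- Total variance: 15^2/12 = 18.75.
- Share kept: 12.5/18.75 = 0.67, a loss of 33%.

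Other assumed shapes, truncated to 0-15:

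| Shape | Share kept | Loss |
|---|---|---|
| Normal, mean 4 to 6, SD 3 or 4 | 0.61-0.67 | 33-39% |
| Normal, mean 7, SD 3 or 4 | 0.54-0.58 | 42-46% |
| Normal, mean 8, SD 3 or 4 | 0.45-0.53 | 47-55% |
| Exponential, scale 3, 5 or 8 | 0.67-0.71 | 29-33% |

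The largest loss (55%) needs 84% of participants above the cut. Roughly 30-45% is a fair summary.

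**The case against.** The strongest reply is that the regression is one sentence behind the primary test and serves none of the listed objectives or endpoints. Multiplicity handling, an overall test and the coding of graded examinations commonly sit in a statistical analysis plan, which is not at hand. The threshold is written next to the paired t-test, and the protocol does not say that factors are picked by unadjusted p-values. An overall test held elsewhere would bring the rate to about 5%.

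Much of this stands, and it limits the weight of the point. It does not remove it. The protocol itself fixes the nine factors, the aim of picking out which ones matter, and the two-group AHI, and it offers no other threshold. An analysis plan that followed it would inherit all of these.

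The cut at 5 also has a rationale. An exclusion criterion on the Epworth score applies only at AHI 5-15, and the pilot was reported by primary snoring and mild OSA. That supports a descriptive table, but it does not recover the lost information.

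Two stronger readings are tempting. A reader might infer a much higher error rate by counting every category of the graded examinations as a separate test. The grading sheets are not shown, and a categorical factor is normally tested jointly, which leaves nine tests. A reader might also multiply the nine tests over several outcomes. The protocol refers to a single outcome without saying which, and repeated partner scores would not be independent. Neither reading is supported.

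**Conclusion.** The point holds as a minor-to-moderate one. With no true effects, one outcome, one test per factor and no overall test, the rule as written names at least one factor in about one trial in three (31-37%). The AHI split loses roughly 30-45% of that variable's information. This second figure assumes a roughly linear effect and a distribution that the protocol does not give; the shapes tried ran from 29% to 55%.

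A reader might infer that the trial's main conclusion is in doubt. It is not: the paired primary comparison does not use this regression, and the AHI loss concerns one covariate in a secondary model.

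**What to change.** In the regression sentence of the Statistical Considerations:

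1. Enter the two-night average AHI as a continuous value, and keep the <5 and 5-15 groups for descriptive tables.
2. State that the regression is exploratory.
3. Test the overall F first. This holds the chance of a false factor at about 5% only when no factor has an effect. It does not protect the remaining factors once one is real, which is a further reason for the exploratory label.
4. Report all nine factors with 95% confidence intervals instead of a list selected at P<0.05.

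A compulsory adjustment across the nine factors is not needed for an exploratory model, and step 3 of the working shows its cost in power. How to code the graded examinations can be left to the analysis plan.

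The change costs wording only: no visits, measurements or participants are added. The downside is that fewer factors will be named, and the AHI result becomes a slope instead of a group contrast.

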#### Primary Endpoint:

- A. Reduction of 20 % in the percentage of time spent snoring at levels greater than 40 dB. This will be achieved using WatchPat (510K - K161579) sleep studies
- B. Reduction of 40% in bed partner VAS assessment of snoring.

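### The regression for factors related to response omits the baseline value of the outcome, so AHI group may be flagged as a predictor of snoring change when it has no effect on response

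*Protocol*

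**What the plan says.** Protocol, Statistical Considerations: "Multiple regression analysis will be used to identify which of the following factors has a causal relationship with the outcome". The factors are "age, sex, BMI, neck size, AHI group (<5 and 5-15) and clinical examination characteristics". The examination items are endoscopy staging, Muller manoeuvre, Friedman class and tonsil size, which makes 5 + 4 = 9 factors. The same section gives "Sample size: 50 participants" and, for the main comparison, "Data will be analyzed based on two tailed paired t-test, with 80% power". It does not say which endpoint the regression's outcome is, or whether it is a change, a post-therapy value or a responder status.

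The efficacy endpoints are reductions from baseline. Primary endpoint A is a reduction in the percentage of time snoring above 40 dB. Primary endpoint B is "Reduction of 40% in bed partner VAS assessment of snoring". The secondary endpoints are reductions in ESS and PSQI.

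AHI is taken from the two-night home study under Screening: "If the average AHI from these 2 days is below 15/h", the participant goes on to clinical examination. No other sleep study is scheduled before therapy, and the End of Therapy Review calls the later one a repeat. The pre-therapy snoring value described under Snoring Sound is therefore from the same two nights as AHI.

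The VAS baseline is a separate partner diary over day -14 to -1.

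**The concern.** A change score contains the baseline measurement error with a negative sign. If a listed factor shares that error, the regression finds an association between factor and change that has nothing to do with response. AHI group is such a factor for WatchPAT snoring: two unusually bad nights can raise both AHI and snoring time, and the later return towards the usual level is then credited to the AHI 5-15 group.

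There is a second route. If the device removes a constant fraction of snoring, heavier snorers lose more percentage points. Any factor correlated with baseline snoring will then appear to predict the absolute reduction.

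At stake is the conclusion on who responds, in particular AHI below 5 against AHI 5-15, which the protocol words as a causal finding. The test of whether snoring falls at all is not at stake.

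**Working it through.** **Inputs from the protocol.** N = 50; nine factors; significance at P < 0.05; AHI and objective snoring baseline from the same two nights; a planned fall described as "detect 20% reduction in snoring time from 50% to 30% with 80% power", which is (50 - 30)/50 = 40% in relative terms.

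**Assumed inputs (none is in the protocol).** R = two-night reliability of each measure; rT = correlation of true AHI with true snoring; rE = correlation of their errors on the shared nights; p = fraction of snoring removed (p = 0 stands for a constant effect). AHI group has no effect of its own. Snoring is in SD units of the observed baseline, variables are normal, and the AHI groups are of equal size, so they differ by 2 x sqrt(2/pi) = 1.596 SD of measured AHI.

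**Step 1: expected spurious group difference, outcome = post minus pre.**
- Without baseline: D0 = -1.596 x [rE(1 - R) + p x rT x R].
- With baseline: D1 = 1.596 x (1 - p) x R(1 - R)(rT - rE) / (1 - 0.637 r^2), where r = rT x R + rE(1 - R) and 0.637 = 2/pi.

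Example with R = 0.7, rE = 0.6, rT = 0, p = 0:
- D0 = -1.596 x 0.6 x 0.3 = -0.287.
- r = 0.18, so D1 = 1.596 x 0.21 x (-0.6) / (1 - 0.637 x 0.0324) = -0.201/0.979 = -0.205.

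**Step 2: simulation at R = 0.7** (N = 50, AHI group plus eight other covariates, 2,000 runs per setting), set against the formulae.

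| p | rE | rT | D0 formula / simulated | D1 formula / simulated | Flagged without -> with baseline |
|---|---|---|---|---|---|
| 0 | 0 | 0 | 0 / -0.002 | 0 / 0.004 | 5.2% -> 5.0% |
| 0 | 0 | 0.3 | 0 / -0.001 | 0.103 / 0.103 | 4.4% -> 6.2% |
| 0 | 0.3 | 0.3 | -0.144 / -0.137 | 0 / 0.006 | 7.8% -> 5.0% |
| 0 | 0.6 | 0 | -0.287 / -0.292 | -0.205 / -0.209 | 20.2% -> 12.7% |
| 0 | 0.6 | 0.3 | -0.287 / -0.288 | -0.111 / -0.109 | 21.1% -> 7.6% |
| 0.4 | 0 | 0.5 | -0.223 / -0.23 | 0.109 / 0.107 | 11.6% -> 7.4% |
| 0.4 | 0.6 | 0.5 | -0.511 / -0.509 | -0.024 / -0.026 | 44.4% -> 5.2% |

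**Step 3: ranges.**
- R 0.7-0.8, rT 0-0.5, rE 0-0.5, about nine terms. Without baseline: 5-16% (change, constant effect), 5-38% (change, 40% proportional effect), 4-50% (post-therapy value as outcome). With baseline, in the change models: 4-11%.
- A wider set of assumptions (R 0.5-0.9, rE 0-0.6, rT 0-0.5). Constant effect: 4-32% without, 4-15% with. Proportional effect: 6-44% without, 5-8% with.

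The upper ends move with the assumptions. The direction is the same in both sets.

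**Step 4: when adjustment helps and when it does not.** D1 is zero when rT = rE; for p = 0, D0 is zero only when rE = 0. Ignoring the small denominator term, for p = 0 adjustment reduces the bias when R|rT - rE| < rE. It fails to do so when rT exceeds rE(1 + 1/R), which is 2.43 rE at R = 0.7. With true correlation and no shared error, adjustment raises the false-flag rate from about 5% to 9-11% in the first set of assumptions.

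**Step 5: the undefined outcome.** With baseline in a linear model, the AHI-group coefficient is identical whether the outcome is post-therapy value or change, since the two differ only by the baseline itself. Without baseline they differ, even in sign. At R = 0.7, rT = 0.5 and a constant effect, the post-therapy coefficient is 1.596 x 0.5 x 0.7 = +0.559 (simulated 0.548), while the change coefficient is zero or negative.

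**The case against.** **Full model specification is often left to an SAP, which is not at hand.** This is fair, and the list is not expressly called complete. But the protocol does fix the candidate factors by name, so adding baseline amends a stated choice. It does not fill a silence.

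**The outcome is undefined, and the argument assumes a change score.** This stands in part. For a raw post-therapy value, shared-night error alone produces no bias without baseline (about 4% flagged); there a true AHI-snoring correlation is what inflates the rate. Responder status and percentage reduction were not examined. Under a proportional effect, part of the group difference is real on the absolute scale, because heavier snorers do lose more points. It still says nothing about AHI as a driver of response.

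**Adjustment is not a cure.** This is correct. Baseline is measured with error, so shared-night bias is only partly removed (20.2% to 12.7% in one setting), and harm is possible when there is true correlation without shared error. The worst case without baseline is nevertheless much larger than the worst case with it.

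**The ESS exclusion.** A reader might infer that "ESS > 10 in participants with AHI 5-15/h" truncates baseline ESS in one AHI group by design and so biases the ESS regression as well. The protocol does not establish this. Exclusion criteria are reviewed at the recruitment visit, before the pre-therapy period, while baseline ESS is taken on Day -1; whether one score serves both purposes is not stated. If it does, false flagging under assumed ESS distributions is 5-14% with no treatment effect and 8-37% with a 30% proportional fall, against 4-6% with baseline. If the scores are separate and there is no true change, the rate is about 5% without baseline and 7-10% with it.

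**Reach.** Neither mechanism acts directly on the partner VAS, whose baseline is a separate diary.

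**Conclusion.** The point holds as a minor one. The listed factors omit the baseline of the outcome, and AHI group shares its nights with the objective snoring baseline, so AHI group may be flagged as a predictor of snoring change without any effect on response. The rate is about 5-38% without baseline and 4-11% with it, given reliability 0.7-0.8, true correlation 0-0.5 and shared-night error correlation 0-0.5. All three are assumptions.

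A reader might go further and infer that AHI group will be flagged. The documents do not support that: the false-flag rate stays near the nominal 5% when there is neither shared-night error nor true correlation, and the protocol gives no figure for either. Nor does the point show a bias in the VAS analysis, and the ESS version is conditional on a fact the protocol leaves open. Grouping AHI at 5 and leaving the nine P values unadjusted are choices that need not change on this account. The paired primary tests, and so the efficacy conclusion, are untouched.

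**What to change.** In Statistical Considerations:
- Name the outcome of the regression for each endpoint analysed.
- Add its baseline value to the model: screening percentage of sleep time snoring above 40 dB for endpoint A, and pre-therapy mean VAS for endpoint B. The VAS term is routine adjustment, with no specific bias shown.
- Describe the factor results as exploratory associations.

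The cost is a sentence or two and no new data. With one term per factor and complete records, residual degrees of freedom fall from 50 - 1 - 9 = 40 to 39. The text should acknowledge that adjustment for an error-prone baseline is incomplete and can raise the false-flag rate slightly (about 5% to 9-11%) if AHI and snoring are truly correlated with no shared-night error.
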